This IRB application also covers a secondary study, to additionally study biological correlates of antenatal anxiety (i.e., immune and endocrine functioning) in a subset of women from the main trial: 200 drawn from our randomized trial (100 intervention, 100 usual care), as well as 100 healthy women without anxiety or depression. The aims of the secondary study are as follows:

**Aim 1:** To characterize the “immune phenotype” of anxious women across the peripartum, specifically by measuring the relation among anxiety symptoms and peripheral markers of inflammation (IL-6, CCL3, CXCL8, Eotaxin, VEGF, and GM-CSF, as supported by our preliminary data) within and across women (both anxious and healthy) and between those receiving the intervention and control.

**Aim 2:** To determine the relation between levels of allopregnanolone (ALLO) in pregnancy and 1) concurrent anxiety symptoms and 2) future symptoms of postpartum depression (PPD).

**Aim 3:** To examine the relation between changes in immune functioning (Aim 1) and ALLO levels (Aim 2) in anxious pregnancy across time.

**Aim 4:** To examine whether immune function and/or ALLO are mediators or moderators of the association between antenatal anxiety and poor birth outcomes (specifically, preterm birth and small-for-gestational age).

To supplement our study, we will collect qualitative data as part of a process evaluation to better understand women's experiences with the intervention (e.g. how it can be improved). Given the recent effects of COVID-19 on our participants and our study, we will also inquire about how the telephone format of our intervention is being received by our participants, as well as try to learn about the impact of social-distancing and other aspects of the COVID-19 situation on pregnant women generally.

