For the secondary biological study, a sample size of 60 subjects in each group, women with anxiety (with and without intervention) and healthy controls, will give us at least 80% power to detect a difference in means of log-transformed cytokines across groups with an effect size of 0.3 to 0.5. This calculation assumes four repeated measurements with exchangeable covariance structure, a correlation of 0.6 and alpha level = 0.05. The smallest observed effect size for CCL3 between anxious and non-anxious women in the preliminary data of 51 women was 0.3 in 1nd trimester to 0.5 in the 2nd trimester (Cohen's D from 0.3 to 0.5). Sample size calculations were performed using the PASS Sample Size Software program.(34) Prior studies in our clinic have an attrition rate of up to 20%, but because the attrition rate for this type of study in Pakistan is unknown we will increase our sample size to account for higher attrition (up to 40%). We will therefore enroll 300 women to yield an ultimate sample size of at least 180.

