#### Analysis of Variables from Biological Substudy

**Statistical Analysis.** Oversight for the statistical analyses will be provided by [name] of the Johns Hopkins Biostatistics Center. The initial statistical approach will include a descriptive cross-sectional analysis at each time point, both for quality assurance and to attain a better understanding of the distributions of the outcome variables for use in subsequent analyses, including the need for any transformations, followed by the longitudinal analyses. For **Aim 1**, we will assess the associations between cytokine levels as dependent variables and level of anxiety (as measured by the HADS) as the independent variable. The level of anxiety will be considered from the following perspectives: 1) dichotomous (above and below HADS=8) and 2) continuous. In both analyses, we will compare women with anxiety vs. healthy controls and with and without the intervention to evaluate whether there is a positive association between

cytokines and other immune markers with anxiety. In addition, we will perform a comparison of immune markers between women disease/intervention groups adjusted for potential confounders that are differentially distributed by disease group, using multivariable linear regression model at each time point. We will assess whether association between immune marker and anxiety is different by group and by visit. In the longitudinal analyses, we will fit generalized linear mixed effect models to account for within-woman correlation of inflammatory markers. The model will include indicators for visit and group as well as any relevant interaction terms (e.g. group by visit). The models will adjust for baseline severity and other patient characteristics. A random effect for woman will be included as a random intercept. Other, more complex model structures will be explored, such as a model with random slope or non-independent residual correlation structure. These models account for missing at random, i.e. missing data are assumed to depend on prior immune marker values and covariates. Standard model checking will be performed and the most parsimonious model will be selected based on the Akaike Information Criterion (AIC).

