For **Aim 2**, we will follow the same approach, with ALLO levels as the independent variables and anxiety as the dependent variable. Generalized linear mixed effects models will be fit to the data to model anxiety trajectories while accounting for within-women correlation of these measures. Estimated anxiety trajectories and ALLO levels will be used as candidate independent variables in a logistic regression model of risk of PPD. Cross-validated area under the curve will be used to assess model discrimination between women with and without PPD.

For **Aim 3**, we will assess the associations between ALLO levels and immune markers at different times during pregnancy by disease/intervention group and will fit similar generalized linear mixed effects models described in Aims 1 and 2. These models will first be fit for each immune marker separately and then combined into a multilevel model with crossed random effects that includes with random intercepts for woman and immune marker to “borrow information” across multiple immune markers within the woman.

For **Aim 4**, our analysis will focus on the association of perinatal anxiety and birth outcomes, specifically assessing mediation in both cross-sectional and longitudinal analyses partitioning the total effect of anxiety on birth outcomes as direct and indirect, through change in cytokine and hormone levels.

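### The combined Aim 3 model, as named, has no woman-by-marker or blood-draw term and no marker-specific ALLO slope, so its pooled slope hides differences between markers and its standard error is generally miscalibrated

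*Combined protocol and SAP*

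**What the plan says.** Under Analysis of Variables from Biological Substudy, Aim 3 relates ALLO levels to immune markers by disease/intervention group. The plan "will fit similar generalized linear mixed effects models described in Aims 1 and 2". It continues: "These models will first be fit for each immune marker separately". After that the models are "combined into a multilevel model with crossed random effects that includes with random intercepts for woman and immune marker", so that markers inform one another within a woman. No other random effect, and no ALLO-by-marker term, is named for the combined model.

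The substudy aims list six markers: "IL-6, CCL3, CXCL8, Eotaxin, VEGF, and GM-CSF, as supported by our preliminary data".

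The Aim 1 text on longitudinal models allows relevant interactions, with group by visit as the only example. It adds: "Other, more complex model structures will be explored, such as a model with random slope or non-independent residual correlation structure". Selection is by AIC.

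The substudy sample-size paragraph assumes "four repeated measurements with exchangeable covariance structure, a correlation of 0.6 and alpha level = 0.05" for a cytokine, with at least 180 women analysed. It concerns a difference in group means. Aim 3 has no power or precision figure of its own. The Missing Data section leaves further detail to a statistical analysis plan to be finalised before unblinding.

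**The concern.** The combined data set has up to 24 values per woman (6 markers × 4 draws), and ALLO varies from draw to draw. Three features of such data have no place in the named model.

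- **Same draw.** Markers from one tube share handling and assay conditions. The plan describes a multiplex kit, up to 8 hours before centrifugation, and 6–8 shipments. ALLO is measured on the same draw, so a shared draw deviation sits at the level at which ALLO varies.
- **Same marker.** A woman who runs high on one marker need not run high on the others. That persistent level is a woman-by-marker component.
- **Different associations.** ALLO may relate to six markers with different sizes or signs. Random intercepts pool levels, so the sharing of information does not reach the association that Aim 3 asks about.

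At stake are the interval and test for the pooled ALLO slope, and what that slope means.

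**Working it through.** Aim 3 states no figure to reproduce, so the check compares the standard error that the named model reports with the true sampling SD of the pooled slope.

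**Inputs from the documents.** 180 women, 4 draws, 6 markers, and correlation 0.6 between repeated values of one marker.

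**Assumptions, not in the documents.** Total variance is 1, split into woman u, woman-by-marker v, draw w and residual e = 1 − u − v − w. Apart from a reference case with v = w = 0, u + v = 0.6 to match the stated correlation. w runs from 0 to 0.3. The share of ALLO variance lying between women is 0.2, 0.5 or 0.8. Group terms are left out.

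**Step 1: correlations.** With total variance 1 and given marker, two values from one woman correlate:
- same marker, different draws: u + v
- different markers, same draw: u + w
- different markers, different draws: u

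The named model has one value for all three. With u = 0.2, v = 0.4, w = 0.1 the truth is 0.6, 0.3 and 0.2. The plan's 0.6 for one marker fits the named model only if different markers also correlate 0.6 within a woman.

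**Step 2: effect on the standard error, in closed form.** A woman's 24 values form 276 pairs: 36 same-marker, 60 same-draw and 180 neither. The single covariance that the named model fits is their average:

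c = u + (36v + 60w)/276

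For the within-woman part of the slope, the model takes the variance of a six-marker draw mean as (1 − c)/6. The true value is w + e/6. The ratio of reported to true SE is the square root of [(1 − c)/6] ÷ [w + e/6].

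Example, u = 0.2, v = 0.4, w = 0.2, e = 0.2: c = 0.2 + (14.4 + 12)/276 = 0.2957. The model has 0.7043/6 = 0.1174, the truth is 0.2 + 0.2/6 = 0.2333, and the ratio is √(0.1174/0.2333) = 0.71.

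Setting the two variances equal gives w = v/6. Only there, or at v = w = 0, is this part of the standard error right.

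**Step 3: simulation of the whole slope.** There were 1,000 datasets per scenario, with REML fits and the marker intercept entered as a six-level fixed factor (near-equivalent in this balanced design). Ranges run over the three ALLO shares and a repeat with 3 draws.

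| u, v, w | Closed-form ratio | Simulated ratio | Coverage of 95% interval |
|---|---|---|---|
| 0.2, 0, 0 | 1.00 | 0.99–1.01 | 95–96% |
| 0.2, 0.4, 0 | 1.37 | 1.22–1.32 | 98–99% |
| 0.2, 0.4, 0.05 | 1.07 | 1.02–1.07 | 95–97% |
| 0.2, 0.4, 0.10 | 0.90 | 0.89–0.94 | 91–93% |
| 0.2, 0.4, 0.20 | 0.71 | 0.70–0.79 | 82–87% |
| 0.2, 0.4, 0.30 | 0.60 | 0.59–0.66 | 76–80% |
| 0.4, 0.2, 0.10 | 0.78 | 0.77–0.81 | 86–89% |

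With woman-by-marker and woman-by-visit intercepts added, coverage was 93% to 97% throughout. A separately written simulation (2,000 datasets, u = 0.2, v = 0.4, ALLO share 0.5) gave ratios 0.0198/0.0151 = 1.31, 0.0197/0.0216 = 0.91 and 0.0195/0.0270 = 0.72 at w = 0, 0.10 and 0.20. With a true slope of zero, its nominal 5% test rejected 1.3%, 7% and 15% of the time.

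**Step 4: one slope for six markers.** With u = 0.2, v = 0.4, w = 0.10 and marker slopes spread about −0.10 with an assumed SD of 0.05, the pooled 95% interval contained the most extreme marker's slope in 9% of datasets. With SD 0.10 it never did. That is what an average does, and it shows why the pooled slope cannot stand for each marker.

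**The case against.** The strongest reply is that the named intercepts need not be the whole model. The text says the combined model includes them, ties Aim 3 to the Aim 1 and 2 models, and for those promises exploration of richer structures with AIC selection. In the scenarios with u = 0.2 and v = 0.4, adding both omitted intercepts improves the expected deviance by about 1,140, 1,400 and 2,180 at w = 0, 0.10 and 0.20, so AIC would choose them if they were tried. This mitigates the gap without closing it. The exploration clause is written for single-marker models, commits to nothing, and mentions neither same-draw correlation nor slopes that differ across markers.

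Several stronger readings are tempting and fail:

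- **That the six assays of a draw are treated as unrelated.** The woman intercept already correlates them. They are independent only given woman and marker. What is missing is the extra same-draw and same-marker correlation.
- **That the plan forces a single ALLO slope throughout.** Separate marker models come first and would show opposite-sign associations. The plan does not say how those results and the pooled slope together answer Aim 3.
- **That the error bars are certainly wrong, or wrong in a known direction.** The size and sign depend on variances that the documents do not give.
- **That variation in slope between markers inflates false positives for markers in general.** The aims name six specific markers, so the relevant target is the average over those six.

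It is also fair that the section answers a request for a brief plan and that detail is deferred. But the combined structure is stated, and the later plan is the place to complete it.

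**Conclusion.** The point holds for the combined model as named. Its standard error for the pooled ALLO slope is correct only when the woman-by-marker and draw components are both zero or happen to offset (roughly w = v/6). Over the assumed ranges it runs from about 30% too wide (ratio 1.32) to about 40% too narrow (ratio 0.59). These figures rest on the assumed variance split, a balanced design and no group terms. They show a plausible range and do not predict this trial's error. Separately, the single slope is an average that can conceal differences between markers, and the information sharing set up by the intercepts does not apply to that slope. The marker-specific fits limit the harm. The matter is worth settling before analysis, but it touches one aim of a secondary substudy and leaves the primary outcome alone.

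**What to change.** In the statistical analysis plan, specify the combined Aim 3 model as follows:

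1. Log-transform the markers and put them on a common scale, so that an average slope has a meaning.
2. Keep the woman intercept and add random intercepts for woman-by-marker and woman-by-visit (the draw).
3. Let the ALLO slope differ by marker through ALLO-by-marker terms, with one joint test.
4. Report the average slope beside the marker-specific slopes, say that the average refers to these six markers, and state which result answers Aim 3.

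The cost is a few lines of text and a larger mixed model. Intervals for the average slope may widen: in the simulations they did where the draw variance was appreciable, and they narrowed where it was zero and the woman-by-marker variance was not. No data collection changes.

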## Missing Data

Adjusted analysis and subgroup analysis will be based on covariates at baseline without non-missing values. Sensitivity analysis will be performed on the covariates with missing values imputed (133). Detailed imputation methods will be described in the statistical analysis plan. All analyses will be detailed in the statistical analysis plan, which will be finalized before un-blinding the study.

## Baseline Descriptive Statistics

Regarding quantitative data, we will implement reliability and quality control checks, including randomly selected reliability checks on administration (in real time so corrections can be made, not compromising data quality) and scoring/coding of all measures within one week for completeness and accuracy. All questionnaires completed by trained assessment team members will be reviewed for skipped items or ambiguous answers; assessment team members will be asked to correct any missing or ambiguous entries. Data will be double entered. Data files will be checked with software for discrepancies, flagged and corrected. Although we will attempt to minimize the effects of missing data, some data will likely be missing due to maternal non-response at particular time points. Analyses will be conducted to examine the prevalence and patterns of missing data and methods appropriate for dealing with missing data (such as multiple imputation) will be used. All analyses will use an intent-to-treat (ITT) approach, using all subjects randomly assigned to treatment or control groups. Exploratory analyses will investigate whether effects are larger among mothers who participated in more intervention sessions (estimating complier average causal effects)(136). We will also do preliminary analyses to ensure that the randomization succeeded in creating similar groups at baseline. Baseline variables that are distributed unequally between the intervention and control groups will be adjusted for in the parametric models (below). Finally, to document a data collector effects, we will calculate inter-rater reliability (IRR) during the training period and calculate the Intra-class Correlation Coefficient (ICC) to measure differences between data collectors.

## Mediation Analysis

In order to understand the potential mediating effects of stress and social support and women's empowerment in the 3rd trimester (the primary mediators of interest) on CMDs (combined GAD and MDE) at 6 weeks postpartum, we will estimate direct and indirect (i.e. mediated) effects of the intervention using a model-based mediation package by Kosuke Imai (138). At a simple level, these mediation methods can be thought of as estimating a series of regression models, which we will use to test beliefs about the underlying process relating the mediating variables to the outcomes. Because mediation analyses depend heavily on some key identifying assumptions and the specific model forms and variables included in the models, we will do extensive diagnostics and sensitivity checks (e.g., goodness of fit tests, exploring alternative specifications and variables to be included). A benefit of the Imai et al. mediation package is that it has built-in sensitivity analyses to the key assumptions, such as that of sequential ignorability of the mediator (that the mediator values are independent of the potential outcomes, conditional on the treatment and observed covariates). All analyses within this aim will be exploratory given limited power for detecting these interaction effects and difficulties in interpreting mediational effects as causal (139).

## Moderator Analysis

To examine potential effect modifiers of the intervention treatment effects on birth outcomes, we will expand the regression models to include a term for the interaction between intervention group status and the potential moderators (exposure to social support, stress levels, marital relationship and empowerment measured at baseline as well as retrospective report of IPV measured at 6 weeks postpartum). This will allow us to examine whether the effects of HMHB differ for mothers (or their children) with varying levels of the potential moderators; analyses will be informed by recommendations in Aiken and West (1991)(140) and Preacher et al. (2006) (141). This aim will be exploratory given limited power for detecting interaction effects.

5. **Answer the following if they are relevant to your study design:**

- If the study has different arms, explain the process for assigning participants (intervention/control, case/control), including the sequence and timing of the assignment.

Study statistician will produce a random sequence of assignments to the study arms. This sequence will be generated using a pseudo random-number generator, and will be constructed using randomly permuted blocks of size 4, 8, 12, and 16. The assignment list will be printed in order, with each step of the sequence separately stored in opaque envelopes and numbered sequentially. When an individual who has been determined as eligible via the screening procedure subsequently provides consent for study participation, the X will pull the next available envelope, opening it, and recording the assignment to intervention or control.

In addition to the participants randomized through the main study, there will be three arms for the biological study. We will choose the first 100 participants each in the intervention and control arms, and will also recruit a group of 100 healthy controls (HADS <8) who will participate only in the biological study.

- If human biospecimens (blood, urine, saliva, etc.) will be collected, provide details about who will collect the specimen, the volume (ml) and frequency of collection, how the specimen will be used, stored, identified, and disposed of when the study is over. If specimens will be collected for use in future research (beyond this study), complete the "Biospecimen Repository" section below.
-

**Biological Outcome Variables:** Subjects will have their blood drawn (up to 20 ml) at all four visits by a study clinician or a research assistant trained in phlebotomy. Each participant will be scheduled as close to possible to the same time of day during the morning hours for all four blood draws (as blood is drawn in HFH between 8:00am and 1:00 pm), allowing us to control for diurnal variation in cytokine levels. Blood will be collected in sodium-heparin tubes for immune cell preparation. Blood will be centrifuged within 8 hours of collection by low-density gradient centrifugation via a Z326 High Performance Centrifuge. Plasma will immediately be frozen in cryovials at -80 C in a ThermoScientific Revco RLE Ultra-Low Lab Freezer and will be stored there until it is shipped to Baltimore for analysis at the end of the trial.

**Shipping of Samples:** Plasma samples (approximately 4800 cryovials) will be shipped from Pakistan to Baltimore at the end of the trial for analysis using Federal Express courier services. Blood will stay frozen at a minimum of -20 throughout shipment, using standard cold packs, dry ice, or liquid nitrogen as required by local regulations and the standards of the courier services. Because we will not be able to maintain a temperature of -80 during shipping, we plan to use multiple shipments (6-8) so that we can initiate analysis immediately upon arrival in Baltimore to avoid freeze-thaw cycles. (Shipping all vials at once will yield a batch too large for the capacity of our laboratory and staff to process at once.) Leftover samples will be refrozen for possible additional future analyses and will be stored in [name] lab at the Women's Mood Disorders Center, Johns Hopkins School of Medicine.

**Blood Sample timing:** Targets times for sampling blood will be at baseline (between 10 and 22 weeks), during the second trimester (24 weeks  $\pm$  2), the third trimester (36 weeks  $\pm$  2) and at 6 weeks  $\pm$  2 postpartum). All samples will be drawn in the morning (between 8:00 am and 1:00 pm) to minimize differences due to diurnal fluctuations in cytokine levels.

- If genetic/genomic analyses are planned, address whether the data will be contributed to a GWAS or other large dataset. Address returning unanticipated incidental genetic findings to study participants.

N/A

- If clinical or laboratory work will be performed at JHU/JHH, provide the JH Biosafety Registration Number.

[BC1512080301 \(BSL1\)](#) and [B1512080101 \(BSL2\)](#).

- If you will perform investigational or standard diagnostic laboratory tests using human samples or data, clarify whether the tests are validated and/or the lab is certified (for example is CLIA certified in the U.S.). Explain the failure rate and under what circumstances you will repeat a test. For all human testing (biomedical, psychological, educational, etc.), clarify your plans for reporting test results to participants and/or to their families or clinicians. Address returning unanticipated incidental findings to study participants.

**Cytokine Analysis.** Cytokine analysis will take place in the Becton Dickinson Immune Function Laboratory of the JHBSPH. Plasma cytokines will be measured using the Meso-Scale Discovery (MSD; Gaithersburg, MD) Ultrasensitive Proinflammatory multiplex kit. The MSD multispot array will be run according to the manufacturer's protocol. Calibration curves will be prepared. Plates will be read using the MS2400 imager (MSD). Samples for each case and

matched control will be assayed adjacently, but in random order and in replicate. To determine assay reliability, we will calculate the coefficient of variation (CV%) for each woman's replicates when both have concentrations above the LOD.(46)

**Hormone Analysis.** All hormone analyses will take place in The Clinical Research Unit Core Laboratory at the Johns Hopkins Bayview Medical Campus. The Core also includes a Sample Processing Laboratory. Directed by [name], a professor in the Division of Geriatric Medicine and Gerontology, the laboratory offers 87 distinct assays of clinical chemical endpoints and biomarkers to support university research protocols. ALLO will be analyzed with the EIA kit from Arbor Assays LLC Cat 3 KC44-H1. Progesterone will be analyzed with EIA kit from Alpco catalogue # PROHU-E01.

- If your study involves medical, pharmaceutical or other therapeutic intervention, provide the following information:

1. Will the study staff be blind to participant intervention status?

The proposed study is a single-blind, individual randomized clinical trial. The assessment team, trial statistician, and PIs will be masked to allocation status of study participants. To maintain masking during the trial, intervention and assessment teams will not have any interaction during the trial, as they will be placed at separate locations within the Obstetrics Department of HFH. Furthermore, participants will be instructed not to disclose which type of treatment they are receiving to the assessment team. Fidelity of masking will be measured by having assessors guess the trial arm of each participant at the end of follow-up assessment. We hypothesize that assessors will only be able to correctly guess the condition of participants at a chance rate of nearly 50% at follow-up assessments, indicating that masking is maintained.

2. Will participants receive standard care or have current therapy stopped?

Each woman randomized into the HMHB intervention arm will receive the HMHB intervention program plus usual care. Women allocated to the control condition will get usual care (slightly enhanced) alone. The WHO recommends eight antenatal visits for positive pregnancy experience (43) which we will be the target number of visits for study participants in the control group (depending on their gestational week). These visits will involve evaluating health status, discussing any concerns, and performing routine exams consistent with stage of pregnancy. Usual care will also be enhanced by medical staff at the hospital receiving additional training in mental health treatment to counsel participants. Transportation will also be provided or facilitated for participants to assist with attending appointments and the study will pay for any ultrasounds needed.

3. Will you use a placebo or non-treatment group, and is that justifiable?

The control arm will receive a slightly enhanced version of usual care, which we consider is justifiable.

4. Explain when you may remove a participant from the study.

Missed sessions or early withdrawal (i.e., withdrawal before all sessions are completed) from the HMHB intervention or from the schedule of visits for the control group, will not result in investigator/research team-initiated withdrawal from the study; in such cases of missed visits, remaining study procedures can and should be completed as indicated by the study protocol. If a clinically significant finding is identified (including but not limited to changes from baseline) after enrollment, the HBHM trainer, assessor or hospital staff will refer the case to Co-I [name] (a psychologist and the main intervention supervisor) and Co-I [name] (a psychiatrist and the main field supervisor) to determine if any change in participant management is needed. Any new clinically relevant finding will be reported as an adverse event (AE).

Participants are free to withdraw from the study at any time upon request. An investigator may discontinue or withdraw a participant from the study for the following reasons:

- Death of participant.
- Women who develop suicidal ideation who are unable to participate because of their care
- Participant moves from the study area.
- Acute, chronic, or long-term physical or psychiatric illness in the participant leading to inpatient hospitalization during the study
- Any clinical AE, laboratory abnormality, or other medical condition or situation occurs such that continued participation in the study would not be in the best interest of the participant
- Disease progression that requires discontinuation of the intervention

The reason for participant termination or withdrawal from the study will be recorded. Women with a miscarriage, stillbirth or neonatal death before the 6 week postpartum visit will still be included in the study for the 6 week postpartum mental health outcomes, although they may not be able to provide data for other child-related outcomes.

A participant will be considered lost to follow-up if he or she fails to return to the endpoint assessment (i.e., 6 weeks postpartum) and/or is unable to be contacted by the study site staff.

The following actions will be taken if a participant fails to return to the clinic for a required study visit:

- The study team will attempt to contact the participant, reschedule the missed visit in a subsequent week, counsel the participant on the importance of maintaining the assigned visit schedule, and ascertain whether or not the participant wishes to and/or should continue in the study.
- Before a participant is deemed lost to follow-up, the investigator or designee will make every effort to regain contact with the participant (where possible, three telephone calls and a call to any designated family friends for whom the participant has provided a contact phone number in case of loss to follow-up, and if necessary, a certified letter may be sent to the participant's last known mailing address). These contact attempts will be documented in the participant's study file.
- Should the participant continue to be unreachable, she will be considered to have withdrawn from the study as lost to follow-up.

